
CLBP (Airaksinen et al., 2006) (NICE, 2009), the healthcare profession continues to request further

investigations to explain symptoms radiologically. Various publications have addressed strategic plans

to reduce the imaging rates for NS-CLBP patients (Jenkins et al., 2015).

A recent qualitative study suggested that patients were more relieved following MRI and that a

radiological diagnosis of NS-LBP may result in increased feelings of guilt (Serbic and Pincus, 2014).

On the other hand, the blinding of acutely diagnosed LBP patients to MRI results has been associated

with a better sense of wellbeing (Ash et al., 2008). Nonetheless, the ordering of MRI for NS-LBP

patients was not associated with an improvement in patient management; it merely increased the

workload for primary care physicians (Kendrick et al., 2001).

The role of post-procedural information

A study by McCullough et al. (2012) indicated that the inclusion of an epidemiological information

statement along with the MRI report resulted in a decrease in narcotic prescriptions. Moreover, re-

wording the medical terminology of the MRI report with more understandable and less threatening

terms resulted in less emotional distress and increased the comprehension of the report by the patients

(Bossen et al., 2013).

Clinicians may ignore the clinical guidelines for CLBP imaging for multiple reasons that relate

primarily to the specific patient and physician. As described by Serbic and Pincus (2014), patients may

display urgency, requesting a more advanced diagnostic tool; those patients are relieved to finally

receive a diagnosis, even when false positive results are obtained. Likewise, doctors may also hold

certain beliefs regarding radiological diagnoses and their understanding of the usage of diagnostic

tools for NS-LBP.

There is compelling evidence that MRI for NS-CLBP does not predict improvement in patient

functional improvement, but instead is associated with increased prescription of pain medication and

clinic visits.

Page 9 of 28

The role of psychological factors and the chronicity

Psychological factors, such as depression and fear, are strong predictors for chronicity and non-

recovery (George and Beneciuk, 2015). Painful experience can be likened to memory rather than

patho-anatomical process, which are suggested by (Taylor et al., 2015) using functional MRI for the

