cortical representation of neuron firing in chronic pain patients how found that these patients display

more neurons firing in the memory area when they asked to imagine doing daily activities whereas

control group showed more firing in the motor areas. Chronic back pain patients tend to display a

heightened fear of movement (kinesiophobia) and increased depression (George and Beneciuk, 2015).

The Saudi Arabian context

The healthcare system in Saudi Arabia is government-funded and publically available to all; 79% of

all patients receive treatment in the public system while the remainder are treated privately (Almalki et

al., 2011). Insurance companies cover the majority of private patients. The public healthcare system is

structured into three levels: primary, secondary and tertiary. Advanced radiological investigations are

not available at the primary level.

CLBP patients in Saudi Arabia have the option of directly seeking medical treatment in the private

system, thus bypassing the primary triage level. A study performed in a 440-bed university hospital in

the eastern region of Saudi Arabia showed that the average number of MRI assessments performed

annually was 2725, with the highest proportion attributed to adult orthopaedic and spine referrals;

these figures have increased yearly since 2007 (Jabali et al, 2015). This hospital is considered small in

comparison to the referenced medical cities in the region, which serve 1200 beds. Nonetheless,

university hospital practitioners could be expected to have a good awareness of the literature and

guidelines.

McCullough et al. (2012) demonstrated that lower back pain patients who receive MRI reports without

also receiving information of the likelihood of false positive results were more likely to be prescribed

pain medication than those who had received information on asymptomatic prevalence. The increased

prescription of medication was associated with increased symptoms. With the knowledge that

psychological factors have a significant influence in NS-CLBP, and that MRI results can instigate a

Page 10 of 28

change in symptoms as well, it will be interesting to determine whether pain is preceded by

psychological changes.

STUDY OBJECTIVES AND PURPOSE

PURPOSE

This study aims to identify the psychosocial factors associated with MRI diagnosis in patients with

non-specific low back pain. It will explore the experience of this group of patients in Saudi Arabia and

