Dissolution of the study is unlikely, however if the ethical approval is withdrawn then the

study will be terminated.

DATA ANALYSES

Methods

In Part I of the study, the qualitative part, the FG or interviews will be audio recorded and then

transcribed verbatim to be analysed thematically using Framework analysis (Ward et al., 2013). The

Nvivo software programme will be used later for coding and management.

In Part II of the study, the quantitative part, the Statistical Package for the Social Sciences (SPSS) will

be used for analysis. The process evaluation will require interviews with both healthcare professionals

and trial participants (patients) and analysis of recruitment process documentation completed by the

research team.

Page 18 of 28

All study data will be analysed using the University of Nottingham (UoN) computers and it will be

stored in the UoN server.

Sample size and justification

Part I (FG or interviews): A purposive sampling method will be utilised. In this study, a subgroup of

the populations, healthcare professionals with experience in the management of chronic LBP and

people with chronic LBP, will be identified and then select cases from this subgroup will be

recognised in a purposive manner. Both the patients with chronic LBP and the healthcare professionals

will be intentionally and purposefully chosen according to the inclusion and exclusion criteria defined

earlier.

Part II: since this is a feasibility study a sample size calculation is not required, however a realistic

target of 30 participants estimated based on audit data from recruitment centre, which suggest 80

people with general spine problems are seen in each clinic per month. Assuming two third are not

eligible and further 50% refused consent, we will recruit patients for 6 week from two clinics. The

sample size for each arm of the feasibility RCT will be 15 participants.

Process evaluation interviews will involve 4-6 participants and 2-4 healthcare practitioners.

ADVERSE EVENTS

Since no adverse events (AE) are expected to occur because of participating in the study, no AE data

will be collected. However, since the study will be exploring peoples' experiences, some individuals

may become emotional and uncomfortable with sharing their experiences. If this occurs, the researcher

will stop the discussion and ask that participant if he/she is willing to continue with the discussion.

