Again, they will have the option to withdraw from the study if they feel it is appropriate to do so. If

participants are very distressed, they will be referred to their GPs.

PROCESS EVALUATION

We will conduct a process evaluation alongside the feasibility RCT to explore the acceptability of

randomisation and the study design with both healthcare practitioners involved in trial delivery and

Page 19 of 28

The Psychosocial Impact of MRI Diagnosis in Chronic Non-Specific Low Back Pain

Study ID/ Psychosocial -Factors

patient participants. Interviews will also explore the broader social, political, economic and environmental (context) aspects that may have influenced trial delivery and intervention implementation. The process evaluation will use quantitative data from the recruitment process collected by the research team and qualitative data from participants' interviews.

Quantitative data:

The participating centre will be described in term of number of doctors, supporting staff and caseload.

The number of participants will be recorded to describe the rate of participation, attrition and drop out.

Qualitative data:

Interviews will explore the acceptability of the study design to both patient participants and healthcare practitioners involved in the trial delivery. Furthermore, it will explore the contextual aspects of implementing the study.

Telephone semi-structured interview will be conducted by ([name]) with purposive sample of 4-6 patients and 2-4 healthcare practitioners and research staff in each centre participating in the feasibility study.

All interviews will be audio- recorded and transcribed verbatim and analysed thematically using NVivo software. Validity of the obtained data will be assured by triangulating the findings with participants.

ETHICAL AND REGULATORY ASPECTS

ETHICS COMMITTEE AND REGULATORY APPROVALS

The study will commence after the study protocol, consent form and participant information sheet are approved from the (REC). Modification of the protocol after REC approval will require another full review of all of the documents. If the amendment involves eliminating an adverse event to the participants, the REC will be notified immediately and an updated approval will be sought. Amendments that do not have a major effect on the protocol might be implemented first and REC subsequently notified.

The study shall follow the Declaration of Helsinki (1996) in the Ethical Principles of Conducting

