
DATA PROTECTION

The study staff shall adhere to the Data Protection Act (1998). Participant privacy and informed

consent shall be guarded throughout the study. The CRF will only be used to collect the required

information from the participants for the study. Access to the CRFs is limited to study staff and

regulatory authority. All of the information shall be held is a secure cabinet in a locked room. For the

computer data, all data will be stored in a web-based server with access restricted by user

identification.

Medical information in the patient files will follow the hospital regulations in terms of confidentiality

and how long the information is kept.

QUALITY ASSURANCE & AUDIT

INSURANCE AND INDEMNITY

As a research sponsor, The University of Nottingham insures the study staff, participants and the

protocol with public obligations and clinical trial research.

STUDY CONDUCT

The study will conduct a systematic audit of the major documents, which include adherence to

protocol procedures, consent procedures, ethical approval of the study, CVs of the study staff, and

responsibility for the study material and equipment.

A nominated designee from the sponsor or study coordinator shall perform a systematic audit at least

annually.

STUDY DATA

A nominated designee from the sponsor or the study coordinator shall constantly monitor the

following: confirmation of consent forms, data storage, scours data confirmation, and a back-up plan

for recovering the information.

The CRF data will be checked regularly against the source data.

A portion of the CRF entries (10% or as per the risk assessment) will be verified by inspection against

the source data. If there is evidence of matching error, a whole or a full audit will be performed.

Study monitoring processes and system audits will be accessible to REC if required.

RECORD RETENTION AND ARCHIVING

The CI will retain all study data for at least seven years and in accordance with GCP guidelines and

the University of Nottingham Code of Research Conduct and Ethics. If for any reason the CI is not

able to maintain these data, a second person will be nominated to be responsible for it.

DISCONTINUATION OF THE STUDY BY THE SPONSOR

The sponsor has the right to discontinue the study in the instance of failure to meet the study goals, safety issues or any administrative reason.

STATEMENT OF CONFIDENTIALITY

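### The rule against collecting any adverse event data covers the randomised part and conflicts with the protocol's own rationale, its outcome and its safety clauses

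*Protocol*

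**What the plan says.** The Adverse Events section gives one rule for the study: "Since no adverse events (AE) are expected to occur because of participating in the study, no AE data" will be collected. The section then deals with one situation, that of a participant who "may become emotional and uncomfortable with sharing their experiences. If this occurs, the researcher" pauses the discussion and asks whether the person wishes to go on. Withdrawal remains open, and if "participants are very distressed, they will be referred to their GPs". Nothing in the section addresses patients in the randomised part between allocation and the end of physiotherapy.

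Other parts of the protocol bear on the rule:

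- **Background.** The section on post-procedural information says that MRI in this condition does not predict "functional improvement, but instead is associated with increased prescription of pain medication and" clinic visits. The section on the Saudi Arabian context adds that the increased "prescription of medication was associated with increased symptoms. With the knowledge that" comes a statement that "psychological factors have a significant influence in NS-CLBP, and that MRI results can instigate a" change in symptoms.
- **Outcome.** The Synopsis includes psychosocial impairments linked to the MRI report in the primary outcome.
- **Part II.** One arm is scanned and discusses the result with a doctor before physiotherapy. The other has physiotherapy without a scan. Each arm has 15 patients.
- **Governance.** The section on ethics committee approvals provides for amendments made to eliminate an adverse event. The section on discontinuation lets the sponsor stop "in the instance of failure to meet the study goals, safety issues or any administrative reason".

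**The concern.** Not collecting adverse events follows from expecting none. The expectation is plausible for a conversation about back pain, apart from the distress that the section itself foresees. It is harder to hold for a trial that allocates patients to receive an MRI report in order to study whether the report has unfavourable consequences. The protocol cannot treat such consequences both as its subject and as grounds for recording nothing.

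Two things are at stake. First, the sponsor's right to stop for safety and the amendment route for an adverse event would have no routine source of information. Second, Part II is meant to test the integrity of the protocol and prepare a definitive trial. Under the rule it would supply no event counts and no trial run of the form and procedure that a larger trial would need. Events not asked about at the time cannot be reliably recovered later.

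This is a stated decision in the protocol, so it is not a detail left to a statistical analysis plan.

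**Working it through.** The protocol gives no adverse event figure to reproduce. The check is mainly a comparison of texts, with a short calculation to show how much recording could tell.

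**Step 1. Does the premise fit the rationale?** The Adverse Events section expects no events from taking part. The background associates MRI with more medication and visits, associates more medication with more symptoms, and says that results can change symptoms. It also cites a finding that "On the other hand, the blinding of acutely diagnosed LBP patients to MRI results has been associated" with better wellbeing. On the other side, the same part of the background reports that patients felt relieved after MRI. The fair reading is that the scan result may have unfavourable consequences, not that it does. That is enough to undercut a rule that rests on expecting none.

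**Step 2. Do the governance clauses have a data source?** The amendment clause and the discontinuation clause both assume that an adverse event or safety issue becomes known. The protocol names no record from which it would. The criteria for terminating the study mention only withdrawal of ethical approval, which differs from the sponsor's list.

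**Step 3. Do other data fill the gap?**

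| Source | What it gives | What it leaves out |
|---|---|---|
| Outcome booklet, before and after physiotherapy | Scheduled psychosocial scores in both arms | Serious events, incidental findings, unplanned care; patients who leave before the second booklet |
| Process evaluation counts | Participation, attrition, drop-out | Events in patients who stay |
| Process evaluation interviews | Views of 4–6 purposively chosen patients on acceptability and context | Systematic ascertainment in all 30 |

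Distress after the report is therefore partly covered. The other items are not.

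**Step 4. What could recording show with 15 per arm?** The input is n = 15 per arm (30 in all), from the section on sample size.

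- Upper bound with no events, one-sided 95%: 1 − 0.05^(1/15) = 18.1%.
- The same, two-sided 95% (Clopper–Pearson): 1 − 0.025^(1/15) = 21.8%.
- For both arms together, n = 30: 9.5% one-sided, 11.6% two-sided.

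The chance of at least one event in an arm of 15 is 1 − (1 − p)^15. The rates p are assumptions, since the protocol gives none:

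| Assumed true rate | Chance of at least one event in 15 |
|---|---|
| 2% | 26% |
| 5% | 54% |
| 10% | 79% |
| 20% | 97% |

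A record would probably show a problem that affects one patient in ten or more. It could not establish that events are rare. Without a record, neither statement can be made.

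**The case against.** The strongest case for the protocol has four parts.

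- **Psychosocial harm is already measured.** Impairment linked to the report is an outcome, and the booklet is completed before and after physiotherapy in both arms. This stands in part: it would be wrong to say that the trial has no data on distress. It does not reach serious events, incidental findings or care sought between booklets.
- **The distress text is not confined to Part I.** It speaks of exploring experiences, so it can also cover the process evaluation interviews that accompany Part II. This stands. It still does not cover the period of treatment.
- **The numbers are too small to estimate rates, and safety is not a listed feasibility objective.** The bounds of 18% and 22% bear this out. It is a reason to report counts descriptively, not a reason to leave events unrecorded.
- **Prescriptions and consultations are care use rather than plainly adverse events, and are hard to capture.** The protocol notes that patients may go directly to private care, so self-report may be incomplete. This stands as a limit on the remedy. These are nevertheless the consequences that the background names.

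A reader might go further and infer that the arm without MRI is exposed to missed disease. From the background's 85% non-specific, one could reckon 0.15 × 15 = 2.25, or about 2 of 15 controls with a specific cause. The document does not support this. The 85% describes patients with low back pain who become chronic in general, whereas the trial admits those with no clear medical diagnosis and excludes neurological impairment. The background also cites guideline consensus that MRI adds nothing to diagnosis in this group. Moreover, the inclusion text for the trial asks for an MRI in the last month, which conflicts with an arm that has had none. Until that is reconciled, it is not even clear that controls are unscanned at entry. The figure should not be used.

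**Conclusion.** The concern holds in a limited form. A blanket rule against collecting adverse event data is extended to a randomised comparison on an expectation that the protocol's rationale, its outcome and two of its governance clauses do not share. The gap concerns serious or unexpected events, incidental findings and unplanned care in Part II. Psychosocial change is partly covered by the booklet and by drop-out counts.

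The statistical gain from recording is modest: a one-sided upper bound of 18.1% per arm if nothing is seen, against no bound at all. The case for change rests more on consistency and on trying out the procedure before a definitive trial. The trial can run without the change, but the missing information could not be recovered reliably afterwards.

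The conclusion assumes that the rule is applied as written to both parts, and that hospital records are not otherwise searched for events, of which the protocol says nothing. It does not require that MRI disclosure harms patients, or that going without a scan does.

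**What to change.** For Part II, replace the no-collection rule with a short record completed in both arms from randomisation to the final booklet, using the same questions at the same time points. It should cover:

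- serious or unexpected events;
- distress that leads to withdrawal or referral;
- patient-reported unplanned consultations and new analgesic prescriptions.

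Report counts by arm to the sponsor and the REC, descriptively and without testing, given the bounds above.

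List any specific spinal diagnosis made after randomisation, with how it was found. Do not compare these diagnoses between arms: only one arm is scanned under the protocol, so a difference could reflect detection alone.

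Reconcile the Adverse Events section with the clauses on amendments and on discontinuation by the sponsor, so that each refers to the same record. Keep the existing distress text for the interviews. None of this alters treatment or any clinical rule.

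The cost is protocol wording, a short addition to the case report form and modest data-entry time. Care use will be self-reported and possibly incomplete, particularly for private care, and this should be stated when the counts are reported.
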